6.3.4 Overall Survival

Overall survival (OS) is defined as the duration of time from the date of study enrollment until time of death. Patients without a death event will be censored at the date survival assessment was last evaluated (e.g., clinic visit, phone call).

6.4 TOXICITY CRITERIA

The following adverse event management guidelines are intended to ensure the safety of each patient while on the study. The descriptions and grading scales found in the revised NCI Common Terminology Criteria for Adverse Events (CTCAE) version 5.0 will be utilized for AE reporting. All appropriate treatment areas should have access to a copy of the CTCAE version

5.0. A copy of the CTCAE version 5.0 can be downloaded from the CTEP website (https://ctep.cancer.gov/protocoldevelopment/electronic_applications/ctc.htm#ctc_50).

7 NIH REPORTING REQUIREMENTS / DATA SAFETY MONITORING PLAN

7.1 DEFINITIONS

Please refer to definitions provided in Policy 801: Reporting Research Events found [here](#).

7.2 OHSRP OFFICE OF COMPLIANCE AND TRAINING/IRB REPORTING

7.2.1 Expedited Reporting

Please refer to the reporting requirements in Policy 801: Reporting Research Events and Policy 802 Non-Compliance Human Subjects Research found [here](#). Note: Only IND Safety Reports that meet the definition of an unanticipated problem will need to be reported per these policies.

7.2.2 IRB Requirements for PI Reporting at Continuing Review

Please refer to the reporting requirements in Policy 801: Reporting Research Events found [here](#).

7.3 NCI CLINICAL DIRECTOR REPORTING

Problems expeditiously reported to the OHSRP in iRIS will also be reported to the NCI Clinical Director. A separate submission is not necessary as reports in iRIS will be available to the Clinical Director.

In addition to those reports, all deaths that occur within 30 days after receiving a research intervention should be reported via email to the Clinical Director unless they are due to progressive disease.

To report these deaths, please send an email describing the circumstances of the death to [name] at [contact] within one business day of learning of the death.

7.4 NIH REQUIRED DATA AND SAFETY MONITORING PLAN

7.4.1 Principal Investigator/Research Team

The clinical research team will meet approximately weekly when patients are being actively treated on the trial to discuss each patient. Decisions about trial continuation will be made based on the efficacy data from prior patients at appropriate time points per the statistical plan.

All data will be collected in a timely manner and reviewed by the principal investigator or a lead associate investigator. Events meeting requirements for expedited reporting as described in section **7.2.1** will be submitted within the appropriate timelines.

The principal investigator will review adverse event and response data on each patient to ensure safety and data accuracy. The principal investigator will personally conduct or supervise the investigation and provide appropriate delegation of responsibilities to other members of the research staff.

8 SPONSOR SAFETY REPORTING

8.1 DEFINITIONS

8.1.1 Adverse Event

Any untoward medical occurrence in a patient or clinical investigation subject administered a

pharmaceutical product and which does not necessarily have a causal relationship with this treatment. An adverse event (AE) can therefore be any unfavorable and unintended sign (including an abnormal laboratory finding), symptom, or disease temporally associated with the use of a medicinal (investigational) product, whether or not related to the medicinal (investigational) product (ICH E6 (R2))

8.1.2 Serious Adverse Event (SAE)

An adverse event or suspected adverse reaction is considered serious if in the view of the investigator or the sponsor, it results in any of the following:

- Death,
- A life-threatening adverse event (see section [8.1.3](#))
- Inpatient hospitalization or prolongation of existing hospitalization
 - A hospitalization/admission that is pre-planned (i.e., elective or scheduled surgery arranged prior to the start of the study), a planned hospitalization for pre-existing condition, or a procedure required by the protocol, without a serious deterioration in health, is not considered a serious adverse event.
 - A hospitalization/admission that is solely driven by non-medical reasons (e.g., hospitalization for patient convenience) is not considered a serious adverse event.
 - Emergency room visits or stays in observation units that do not result in admission to the hospital would not be considered a serious adverse event. The reason for seeking medical care should be evaluated for meeting one of the other serious criteria.
- Persistent or significant incapacity or substantial disruption of the ability to conduct normal life functions
- A congenital anomaly/birth defect.
- Important medical events that may not result in death, be life-threatening, or require hospitalization may be considered a serious adverse drug experience when, based upon appropriate medical judgment, they may jeopardize the patient or subject and may require medical or surgical intervention to prevent one of the outcomes listed in this definition.

8.1.3 Life-threatening

An adverse event or suspected adverse reaction is considered "life-threatening" if, in the view of either the investigator or sponsor, its occurrence places the patient or subject at immediate risk of death. It does not include an adverse event or suspected adverse reaction that, had it occurred in a more severe form, might have caused death. (21CFR312.32)

8.1.4 Severity

The severity of each Adverse Event will be assessed utilizing the CTCAE version 5.

8.1.5 Relationship to Study Product

All AEs will have their relationship to study product assessed using the terms: related or not related.

- Related – There is a reasonable possibility that the study product caused the adverse event. Reasonable possibility means that there is evidence to suggest a causal relationship between the study product and the adverse event.

- Not Related – There is not a reasonable possibility that the administration of the study product caused the event.

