2.3.1.2 Arms

Number	Name	Description
1	Experimental therapy	Avelumab 800 mg IV every two weeks in combination with radiation therapy

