10.3 POPULATIONS FOR ANALYSES

Modified intention to treat: all patients who receive at least one dose of avelumab will be included in the statistical analyses performed.

10.3.1 Evaluable for toxicity:

All patients will be evaluable for toxicity from the time of their first treatment with avelumab.

10.3.2 Evaluable for objective response:

Only those patients who have measurable disease present at baseline and have received at least one dose of therapy will be considered evaluable for response.

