10.4.3 Analysis of the Secondary Endpoints

- CR rate: the fraction of patients who experience a CR or sCR using the study treatment will be determined by dividing the number of these responders by the total evaluable patients. The fraction will be reported along with 90% and 95% two-sided confidence intervals.
- MRDnegCR rate: the fraction of patients who experience an MRDnegCR using the study treatment will be determined by dividing the number of these responders by the total evaluable patients. The fraction will be reported along with 90% and 95% two-sided confidence intervals.
- Reduction of BM and PD plasmacytosis: Percent change in plasma cells in the PB and BM from baseline will be reported descriptively.

- Reduction of size, and/or FDG avidity of extramedullary lesions: Percent reduction of size, and/or FDG avidity, radiographically, of extramedullary lesions compared to baseline will be reported descriptively.
- PFS: will be determined using the Kaplan-Meier method, considering those who progress or die without progression as failures, and censoring those who do not.
- OS: will be determined using the Kaplan-Meier method.
- Safety and tolerability: overall tolerability in terms of adverse events will be evaluated with descriptive statistics to determine the safety of receiving avelumab in the context of irradiation in RRMM patients. NCI CTCAE v.5 will be used to grade adverse events.
- ORR post cycle 1: a milestone ORR at start of cycle 2 will be calculated as above to determine ORR of avelumab monotherapy after 1 cycle of therapy.

Each of these will be calculated starting from the date the patient enrolled onto the trial which corresponds to the date the patient signed the informed consent document. Appropriate confidence intervals will be reported for each of these measures. (Only PFS events occurring during the initiation and of the combination of irradiation and avelumab and after will be counted as this proof of principal study hypothesis is that the combination of BavXRT will be active.)

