10.4.4 Safety Analyses

Early stopping rules for toxicities will be put in place. Specifically, if within the first 6 patients, there are two Grade ≥ 3 toxicities, or if at any time after 6 patients have been treated, the cumulative fraction with Grade ≥ 3 toxicity is 33% or greater, then the trial will suspend accrual and will only reopen following review of the safety data and amendment to modify the treatment appropriately. Adverse events which are clinically insignificant or can be resolved with conservative measures (e.g. laxatives for constipation) or which are not at least possibly due to the experimental treatment will not be included in this early stopping strategy.

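### The toxicity stopping rule in 10.4.4 can understate combination toxicity: its denominator includes patients who have not had XRT, and its attribution term does not match the recorded causality field.

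*Combined protocol and SAP*

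**What the plan says.** Section 10.4.4 sets the suspension rule. The first part reads "if within the first 6 patients, there are two Grade ≥ 3 toxicities, or if at any time after 6 patients have been treated"; the second continues "the cumulative fraction with Grade ≥ 3 toxicity is 33% or greater, then the trial will suspend accrual". Accrual reopens only after a safety review and an amendment. Clinically minor events are left out, as are those "which are not at least possibly due to the experimental treatment will not be included in this early stopping strategy".

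The population comes from 10.3.1: "All patients will be evaluable for toxicity from the time of their first treatment with avelumab". Neither section requires a patient to have received XRT.

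Section 2.3.1.2 names the single arm Experimental therapy and describes it as "Avelumab 800 mg IV every two weeks in combination with radiation therapy". Under 3.1.2, XRT is given in Cycle 2, after one cycle of avelumab alone.

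For causality, 8.1.5 says "All AEs will have their relationship to study product assessed using the terms: related or not related". Section 8.2 adds an alternate etiology for events judged unrelated. Study product is not defined, and avelumab is the only investigational agent named. The safety aim in 10.4.3 is "to determine the safety of receiving avelumab in the context of irradiation in RRMM patients".

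**The concern.** The rule is the plan's only numerical safety boundary, and the question it serves is whether avelumab is safe when given with irradiation. Two features can lower the monitored fraction relative to the toxicity rate in patients who had both treatments.

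- **Denominator.** Patients in the lead-in, and those who leave before Cycle 2, count as treated without any combination exposure. Section 3.5.1 keeps clinically stable patients with biochemical progression on treatment at Cycle 2 Day 1, but that allowance does not extend to overt clinical progression, so some may never receive XRT. For PFS the plan deals with the same issue explicitly: 6.3.3 and 10.4.3 disregard events before the combination starts. The safety rule has no counterpart.
- **Numerator.** The rule filters on one term and the adverse event record is built on another. A Grade 3 in-field radiation injury could properly be coded as unrelated to avelumab, and nothing says which data item feeds the rule.

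At stake is continued accrual while toxicity among patients given the combination is at a level at which the rule would suspend accrual if everyone had been exposed.

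**Working it through.** **Stated figures.** The plan gives no operating characteristics for the toxicity rule. The one it gives for the Simon design reproduces: 0.95^13 = 51.3% early termination at a 5% response rate.

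**Rule as modelled.** Exact sequential binomial up to N = 27, counting affected patients: suspend at 2 or more within the first 6, or when x/n ≥ 0.33 after each patient from the 7th on. With everyone exposed to the combination:

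| True Grade ≥ 3 rate | P(suspend) |
|---|---|
| 10% | 13.0% |
| 20% | 43.9% |
| 30% | 76.3% |
| 40% | 94.3% |

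**Patients in lead-in at any one time.** Accrual is 8-10 per year (10.2), the lead-in lasts 28 days, and up to 14 more days are allowed between cycles (3.2.1).
- 8 × 28/365.25 = 0.61 and 10 × 28/365.25 = 0.77.
- With the full window: 8 × 42/365.25 = 0.92 and 10 × 42/365.25 = 1.15.

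So about 0.6-1.2 patients are in lead-in at a time. With one event-free lead-in patient always in the denominator, P(suspend) at a 30% rate is 69.6% instead of 76.3%. That is an upper bound for one patient, because lead-in patients later become exposed and their own events count.

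**Patients who never reach XRT.** Let f be their share (assumed; not in the documents), q their Grade ≥ 3 rate, and p the combination rate. The rule then monitors f·q + (1 − f)·p. I take q = 10%, close to the 10.2% treatment-related rate in the pooled avelumab monotherapy data (1.2.8). With p = 30%:

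| f | Monitored rate | P(suspend) |
|---|---|---|
| 0% | 30% | 76.3% |
| 10% | 0.01 + 0.27 = 28% | 70.6% |
| 20% | 0.02 + 0.24 = 26% | 64.4% |
| 30% | 0.03 + 0.21 = 24% | 57.8% |

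The loss depends on q being below p. With f = 20% and q = 20%, the monitored rate is 0.04 + 0.24 = 28%, giving 70.6%. With q = 30% there is no loss.

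**Attribution, if the study-product field alone were used.** Suppose a share s of events at a true 30% rate is due to XRT only (s is assumed) and is not counted. The counted rate is 30% × (1 − s).
- s = 10%: 27%, P(suspend) 67.6%.
- s = 25%: 22.5%, P(suspend) 52.6%.
- s = 50%: 15%, P(suspend) 27.0%.

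These figures apply only if the rule is run that way.

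**Effect of a second check.** Apply the 33% threshold also to XRT-exposed patients once six have been treated, with f = 20% and q = 10%:

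| True combination rate | Present rule, all exposed | Present rule, 20% never exposed | With second check, 20% never exposed |
|---|---|---|---|
| 10% | 13.0% | about 13% | about 16% |
| 20% | 43.9% | about 37% | about 47% |
| 30% | 76.3% | about 64% | about 76% |

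**The case against.** A reader might infer that XRT-caused events drop out of the rule. The documents do not support that. Section 10.4.4 filters on the experimental treatment, and 2.3.1.2 describes the experimental arm as avelumab with radiation, so on its own wording the rule counts a radiation injury. It does not refer to 8.1.5. Section 8.2 collects an alternate etiology, where an XRT cause can be written, and under 7.4.1 the team discusses each patient about weekly. This objection stands. What remains is a mismatch of terms: half of the regimen can be captured only as an alternative to the study product, and no sentence connects that entry to the rule.

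A reader might also infer that the rule does not measure combination toxicity at all. That is too strong, because every patient who reaches Cycle 2 counts, with all their events.

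Single snapshots prove little either. If 2 of 13 treated patients had no XRT, 4/13 = 30.8% becomes 4/11 = 36.4%, but only if all four events were in exposed patients. Move one event to an unexposed patient and it is 3/11 = 27.3%. Two patients in lead-in at once is also more than the planned accrual implies on average.

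Finally, counting everyone treated is a defensible choice: the lead-in is part of the regimen and its toxicity matters. That is a reason to keep the all-treated fraction, and it leaves room for a second one among exposed patients.

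**Conclusion.** The point holds in a limited form: the rule can understate combination toxicity.

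The denominator carries most of the weight, because it follows directly from 10.3.1 and 10.4.4. Lead-in patients alone cause modest and temporary dilution. Patients who never reach XRT cause lasting dilution: at a true 30% combination rate, the chance of suspension falls by roughly 6 to 18 percentage points for 10% to 30% never exposed. This rests on two assumptions, that share and a 10% rate in those patients. The 10.2% behind the second comes from solid-tumour patients over their whole avelumab treatment, so a single lead-in cycle in myeloma could differ. If toxicity before XRT equals combination toxicity, there is no dilution.

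The attribution part is a gap to close. XRT events can be missed if the study-product field alone is used, but the text does not require that, and the documents give no figure for the share of such events.

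**What to change.** 1. In 10.4.4, keep the all-treated rule. Add that the same 33% threshold is applied, in numerator and denominator, to patients who have received at least one XRT fraction, starting once six such patients have been treated (the rule's own minimum). Accrual is suspended for review if either fraction meets it.
2. In 8.1.5, 8.2 and the adverse event form, define study product, record relationship to avelumab and to XRT separately, and state in 10.4.4 that an event related to either counts.

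The cost is one extra causality field, a few sentences, and more frequent suspensions. Under the 20% assumption, the chance of suspension rises from about 37% to 47% at a true 20% rate, and from about 13% to 16% at a true 10% rate. Both are close to what the present rule gives when every patient is exposed (43.9% and 13.0%). The sponsor should state these operating characteristics next to the rule.

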8.2 ASSESSMENT OF SAFETY EVENTS

AE information collected will include event description, date of onset, assessment of severity and relationship to study product and alternate etiology (if not related to study product), date of resolution of the event, seriousness and outcome. The assessment of severity and relationship to the study product will be done only by those with the training and authority to make a diagnosis and listed on the Form FDA 1572 as the site principal investigator or sub-investigator. AEs occurring during the collection and reporting period will be documented appropriately regardless of relationship. AEs will be followed through resolution.

SAEs will be:

- Assessed for severity and relationship to study product and alternate etiology (if not related to study product) by a licensed study physician listed on the Form FDA 1572 as the site principal investigator or sub-investigator.
- Recorded on the appropriate SAE report form, the medical record and captured in the clinical database.
- Followed through resolution by a licensed study physician listed on the Form FDA 1572 as the site principal investigator or sub-investigator.

For timeframe of recording adverse events, please refer to section **6.1**. All serious adverse events recorded from the time of first investigational product administration must be reported to the sponsor with the exception of any listed in section **8.5**.

8.3 REPORTING OF SERIOUS ADVERSE EVENTS

Any AE that meets protocol-defined serious criteria or meets the definition of Adverse Event of Special Interest that require expedited reporting must be submitted immediately (within 24 hours of awareness) to OSRO Safety using the CCR SAE report form. Any exceptions to the expedited reporting requirements are found in section **8.5**.

All SAE reporting must include the elements described in section **8.2**.

SAE reports will be submitted to the Center for Cancer Research (CCR) at: [contact] and to the CCR PI and study coordinator. CCR SAE report form and instructions can be found at:

<https://ccrod.cancer.gov/confluence/pages/viewpage.action?pageId=157942842>

Following the assessment of the SAE by OSRO, other supporting documentation of the event may be requested by the OSRO Safety and should be provided as soon as possible.

8.4 WAIVER OF EXPEDITED REPORTING TO CCR

There are no exceptions to expedited reporting requirements.

8.5 SAFETY REPORTING CRITERIA TO THE PHARMACEUTICAL COLLABORATORS

All events listed below must be reported in the defined timelines to [contact]. The CCR Office of Regulatory Affairs will send all reports to the manufacturer(s) as described below, unless otherwise noted.

The investigational agent, avelumab, is being supplied by EMD Serono and the following are their requirements for safety reporting.

The following reportable events must be submitted to EMD Serono within 2 business days or 3 calendar days (whichever comes first) using the applicable safety report form provided. The Principal Investigator/study team will submit reportable events to the Sponsor as well as ensure that any other local reporting requirements are completed, if required (e.g., IRB). The Sponsor will assume responsibility for submitting the reportable event(s) to EMD Serono.

The reportable events to EMD Serono include:

- Serious Adverse Events
- Exposure during Pregnancy or Breastfeeding (even if not associated with an adverse event)
- Occupational exposure (even if not associated with an adverse event)
- Potential drug-induced liver injury (Hy's Law cases): These events are considered important medical events and should be reported as SAEs.

Contact information for submission of reportable events to EMD Serono:

[contact]

OR

E-mail: [contact], specifying:

- PROTOCOL Number and/or Title
- EMD Serono assigned Study Number
- SUBJECT Number
- SITE Number/PI Name

8.6 REPORTING PREGNANCY

8.6.1 Maternal exposure

If a patient becomes pregnant during the course of the study, the study treatment should be discontinued immediately, and the pregnancy reported to the Sponsor no later than 24 hours of when the Investigator becomes aware of it. The Investigator should notify the Sponsor no later than 24 hours of when the outcome of the Pregnancy become known,

Pregnancy itself is not regarded as an SAE. However, congenital abnormalities or birth defects and spontaneous miscarriages that meet serious criteria (section **8.1.2**) should be reported as SAEs.

The outcome of all pregnancies (spontaneous miscarriage, elective termination, ectopic pregnancy, normal birth, or congenital abnormality) should be followed up and documented.

8.6.2 Paternal exposure

Male patients should refrain from fathering a child or donating sperm during the study and for 30 days after study drug.

Pregnancy of the patient's partner is not considered to be an AE. However, the outcome of all pregnancies (spontaneous miscarriage, elective termination, ectopic pregnancy, normal birth, or congenital abnormality) occurring from the date of the first dose until 30 days after the last dose should, if possible, be followed up and documented.

8.7 REGULATORY REPORTING FOR STUDIES CONDUCTED UNDER CCR SPONSORED IND

Following notification from the investigator, CCR, the IND sponsor, will report any suspected adverse reaction that is both serious and unexpected. CCR will report an AE as a suspected adverse reaction only if there is evidence to suggest a causal relationship between the study product and the adverse event. CCR will notify FDA and all participating investigators (i.e., all investigators to whom the sponsor is providing drug under its INDs or under any investigator's IND) in an IND safety report of potential serious risks from clinical trials or any other source, as soon as possible, in accordance to 21 CFR Part 312.32.

All serious events will be reported to the FDA at least annually in a summary format.

